This study will compare the pain experience of the experimental group (CC-ILA) and control group (conventional injection by IANB) during injection and its effectiveness in eliminating pain during extraction of mandibular primary molars in pediatric patients. The null hypothesis is there will be no difference in the pain experience with the use of CC-ILA compared to the IANB in pediatric patients.

AIM OF THE STUDY

Primary aim:

- To evaluate the effectiveness of computer – controlled Intraligamentary Anaesthesia in eliminating pain during extraction of primary mandibular molars compared to Inferior Alveolar Nerve Block.

Secondary aims:

- To assess and compare the pain experience during Local Anaesthesia injection of mandibular primary molars between computer – controlled Intraligamentary Anaesthesia and conventional Inferior Alveolar Nerve Block.
- To assess and compare the pain experience during extraction of mandibular primary molars when using the two different anaesthesia techniques.
- To record the occurrence of any adverse events.

RESEARCH DESIGN

[figure not shown]

Figure (1): Flow Chart Study Design

PLAN OF THE STUDY

Study design

The study will be a two-arm randomized controlled clinical trial. It will be setup and reported according to the CONSORT guidelines.⁽⁴⁰⁾ The PICOT question will be: do pediatric patients aged from 5-7 years (Population; P) assigned to receive CC-ILA (Intervention; I) in comparison to inferior alveolar nerve block conventional injection (Control; C) show less pain during injection and extraction of mandibular primary molars (outcome; O) in twenty-four hours (time; T)?

Study setting and location

Participants will be recruited from Pediatric Dentistry and Dental Public Health Department, Faculty of Dentistry, Alexandria University, Egypt.

Sample size estimation

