The sample size was calculated based on results obtained from previous studies of similar nature. Sample size was estimated assuming alpha error= 5% and study power= 80%. Tekin et al ⁽³⁶⁾ reported mean \pm SD Sound, Eye and Motor (SEM) score = 3.93 ± 1.223 when intraligamentary anesthesia (ILA) was used, and 5.17 ± 1.891 when inferior alveolar nerve block (IANB) was used. Based on comparison of means, sample size was calculated to be 25 per group, and the total sample size required to compare the effectiveness of CC-ILA technique versus IANB during extraction of primary mandibular molars = number of groups \times number per group= $2 \times 25 = 50$.⁽⁴¹⁾ The sample size was calculated using powerandsamplesize.com calculator.⁽⁴²⁾

Criteria for sample selection:

a) Eligibility Criteria

- Age range from 5 – 7 years.
- Children free of any systemic disease or special health care need (ASA I).⁽⁴³⁾
- No previous bad dental experience.⁽⁴⁴⁾
- Positive or definitely positive behaviour during preoperative assessments according to the Frankl Rating Scale (score 3 or 4) (Appendix I).⁽⁴⁵⁾

- Patients whom their mandibular primary molars are indicated for extraction:^(46, 47)
 - Clinical signs and symptoms of pulp degeneration, such as swelling or sinus tracts.
 - Radiographic evidence of periapical or interradicular radiolucency.
 - Non restorable crowns.
 - Failed pulpotomies.
- Patients whose parents will give their consent to participate.

b) Exclusion Criteria for teeth ⁽⁴⁸⁾

- Root resorption affecting more than one third of the root length.
- Fractured roots due to trauma.
- Signs of mobility.
- Ankylosed roots.
- Active sites of pathosis in area of injection that could affect anaesthetic assessment.
- History of allergy to local anesthesia.

Materials

- a) Topical Anaesthesia – Benzocaine gel 20%.*
- b) 27-guage long anaesthetic needles.**
- b) Local anaesthetic carpules: Articaine hydrochloride 4% with adrenaline 1:100,000.***
- c) Equipment:
 - Wand - STA Single Tooth Anaesthesia Device (Figure 2)****
 - Disposable Wand – STA Handpieces with 30-guage 0.5-inch needles. ****
 - Pulse oximeter.*****
 - Dental anaesthetic syringe (non-disposable breech loading, metallic cartridge type).*****
 - Lower Full-crown Extraction forceps.*****

* Dharma Research, Inc. [name].

** C-K Ject, CK Dental Ind. Co., LTD., Korea.

*** ARTINIBSA, Inibsa Dental S.L.U, [name].

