Heart rate (HR) is a physiological sign of pain.⁽⁵⁷⁾ It will be measured using a pulse oximeter. A brief demonstration using the pulse oximeter will be done, and the patient will be instructed to stay still and not to move his hands a lot in order to obtain accurate readings. The pulse oximeter will be placed on the patient's index finger to measure the baseline heart rate (before giving the LA), another measurement will be recorded during LA administration, and during extraction. Readings will be recorded at 2-minute intervals and the mean heart rate measurement will be calculated.

B. Objective method:

Sound, Eye, Motor (SEM) Scale (Figure 3), will be used as an objective method for pain assessment during LA administration and extraction. It comprises the following parameters: (1) Sound, (2) Eye, (3) Motor. For each child, the sounds, eye symptoms and body movements will be evaluated independently by a blind impartial observer using the recorded video tapes. The slightest manifestation of the sound, eyes, or motion of the patient is graded in four levels: comfort, mild, moderate, and severe discomfort, and subsequently given grades 1, 2, 3, 4, respectively. SEM score will be calculated by summing the three grades of the parameters. ⁽⁵⁸⁾

Parameter	Comfort	Mild discomfort	Moderate discomfort	Severe discomfort
Grade	1	2	3	4
Sound	No sound	Non-specific sound (probable pain)	Verbal complaint, louder sound	Verbal complaint shouting, crying
Eye	No sign	Dilated eye without tears (anxiety sign)	Tears, sudden eye movements	Crying, tears all over the face
Motor	Relaxed body and hand status	Muscular contraction, contraction of hands	Sudden body and hand movements	Hand movements for defence, turning the head to the opposite side

Figure (3): SEM scale for the assessment of children's behaviour

Subjective method:

A modified face scale⁽⁵⁹⁾ (Figure 4) from the Maunuksela et al⁽⁶⁰⁾ scale will be used to subjectively record pain during LA injection and extraction. It consists of three schematic faces with different facial expressions for happy and sad faces representing: (A) satisfaction; (B) indifference; and (C) dissatisfaction, respectively. Each child will be trained to use the scale by modelling and then asking each participant to think of the last time she/he felt something painful and to select the facial expression that best represented his/her experience of discomfort.

[figure not shown]

Figure (4): Faces scale modified from the Maunuksela et al scale.

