(A) satisfaction; (B) indifference; and (C) dissatisfaction

II. Assessment of occurrence of adverse events

Parents will be recalled after 24 hours following extraction during follow-up phone calls. Recovery parameter questions will be asked to ascertain the occurrence of lip and cheek biting, post-operative pain, or any adverse events.

STATISTICAL ANALYSIS

All data will be collected; descriptive quantitative values will be summarised using mean and standard deviation, while count and percentage will be used for qualitative values. The data will be represented by suitable tables and graphs. Comparing between normally distributed data will occur using T- and Paired T-tests, while for not – normally distributed data, Wilcoxon signed-rank and Mann-Whitney U tests will be used.

All statistical analyses will be performed with statistical Package for Social Sciences* (SPSS) software version 21.⁽⁶¹⁾ The significance level will be set at $P < 0.05$.

*SPSS Inc., Version 21.0, Chicago, IL, USA

ETHICAL CONSIDERATIONS

The study will be conducted following the ethical principles for medical research involving human subjects in Declaration of Helsinki.⁽⁶²⁾ Ethical approval will be obtained from the Research Ethics Committee, Faculty of Dentistry, Alexandria University before commencing the study.

The objectives, risks and benefits of the study will be explained to parents/ guardians and a signed informed consent will be obtained prior to treatment. (Appendix II). Verbal consent will be obtained from the children before the intervention.

Parents and children will be given age-appropriate oral hygiene instructions including proper teeth brushing twice a day especially before bedtime, as well as flossing if indicated. These measures will be demonstrated on a model. A fluoridated toothpaste and a brush will be provided to each participant on the day of the treatment.

All needed treatment will be provided to the child including any restorations, space maintainers and fluoride application. Post extraction instructions will be explained well to the parents and patients to ensure good wound healing. All the possible clinical and/or adverse outcomes will be explained to the parents and they will be asked to report immediately if any of them occurs.

PROBLEMS ANTICIPATED

1. Lack of compliance from patients and/or their parents.
2. Drop – out of patients during the follow up period.
3. Difficulty in collecting the proposed sample.

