59. Pierro VSdS, Barcelos R, de Souza IPR, Raymundo Jr R. Pediatric bitewing film holder: preschoolers' acceptance and radiographs' diagnostic quality. *Pediatr Dent*. 2008;30:342-7.
61. SPSS I. Statistical package for the social sciences. Data analysis software packages Version. 2012;21.
62. World Medical A. World Medical Association Declaration of Helsinki. Ethical principles for medical research involving human subjects. *Bull World Health Organ*. 2001;79:373-4.

EFFECTIVENESS OF COMPUTER - CONTROLLED INTRALIGAMENTARY LOCAL ANAESTHESIA IN EXTRACTION OF MANDIBULAR PRIMARY MOLARS (RANDOMISED CONTROLLED CLINICAL TRIAL)

Name: [name]

Summary Statement

Sample size was estimated assuming alpha error= 5% and study power= 80%. Tekin et al.⁽¹⁾ reported mean \pm SD Sound, Eye and Motor (SEM) score = 3.93 ± 1.22 when intraligamentary anesthesia (ILA) was used, and 5.17 ± 1.89 when inferior alveolar nerve block (IANB) was used. Based on comparison of means, sample size was calculated to be 25 per group, and the total number required to compare the effectiveness of computer-controlled ILA technique versus IANB during extraction of primary mandibular molars = number of groups \times number per group = $2 \times 25 = 50$.⁽²⁾

Software

[figure not shown]
<http://powerandsamplesize.com/Calculators/Compare-2-Means/2-Sample-Equality>.

References

[name]; B.D.S, M.Sc, Ph.D

Professor of Dental Public Health
Alexandria University
Wednesday, January 20, 2021

IRB NO: 00010556 – IORG 0008839
<https://ohrp.cit.nih.gov/search/search.aspx>

كلية طب الاسنان
 FACULTY OF DENISTRY
 كليته معتمدة

Ethical Guidelines for Conduct of Research on Human Subject

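### The primary aim is to eliminate pain at extraction, but the planned SEM analysis can show only less pain, not how many children were free of it

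*Combined protocol and SAP*

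**What the plan says.** The Abstract (Purpose of the study) and the Aim of the Study (Primary aim) both ask about effectiveness "in eliminating pain during extraction of primary mandibular molars compared to Inferior Alveolar Nerve Block". The Secondary aims list, as a separate item, a comparison of the pain experience at extraction under the two techniques. The null hypothesis at the end of the Introduction is that "there will be no difference in the pain experience with the use of CC-ILA compared to the IANB in pediatric patients", and the PICOT question under Study design asks whether CC-ILA children show less pain.

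Under Study Outcomes (B. Objective method), Sound, Eye and Motor are each graded 1 (comfort) to 4 (severe discomfort), and "SEM score will be calculated by summing the three grades of the parameters". The total therefore runs from 3 to 12, and 3 means comfort on all three parameters.

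The Statistical Analysis section says "descriptive quantitative values will be summarised using mean and standard deviation", with counts and percentages for qualitative values. Comparisons use t tests, or Wilcoxon and Mann-Whitney tests if the data are not normal. No test of proportions is named. The Sample size estimation rests on a comparison of mean SEM, with planning values "score = 3.93 ± 1.223 when intraligamentary anesthesia (ILA) was used, and 5.17 ± 1.891 when inferior alveolar nerve block (IANB) was used".

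**The concern.** The aims treat eliminating pain and comparing pain as two questions, but the analysis section answers only the second. Nothing defines when pain counts as eliminated, and no SEM result states in how many children it was absent. The primary aim would then receive the same answer as the secondary aim on pain at extraction.

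What is at stake is the wording of the conclusion. A significantly lower mean or rank under CC-ILA could be reported as effectiveness in eliminating pain while many CC-ILA children still showed discomfort.

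A related gap concerns children in the CC-ILA arm who have pain and are then extracted under IANB (described under Local Anaesthesia Administration). The plan does not say how they are counted. Such a child could be scored at extraction as a CC-ILA success.

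**Working it through.** **Inputs.** From Sample size estimation: ILA mean 3.93, SD 1.223; IANB mean 5.17, SD 1.891; alpha 5%, power 80%, 25 per group. From Study Outcomes: SEM is an integer from 3 to 12.

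**Step 1: the plan's own figure.** The difference is 5.17 − 3.93 = 1.24 and the average SD is (1.223 + 1.891)/2 = 1.557. With a two-sided test (assumed, because the cited calculator is the two-sample equality one), n = 2 × 1.557² × (1.960 + 0.842)² / 1.24² ≈ 24.8, so 25 per group. The root-mean-square SD of 1.592 gives 26, and the t-test version 27. The stated 25 reproduces, and it is a sample size for a difference in means.

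**Step 2: what a mean and SD say about the share at SEM = 3.** Let X = SEM − 3, an integer from 0 to 9. Assume that the planning scores are extraction scores on this scale. Find the smallest and largest P(X = 0) over all distributions with the stated mean and SD (a linear programme).

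- ILA: E[X] = 0.93 and E[X²] = 0.93² + 1.223² = 2.361.
  - Minimum: mass at X = 0, 1 and 9. Subtracting p₁ + 9p₉ = 0.93 from p₁ + 81p₉ = 2.361 gives p₉ = 0.020 and p₁ = 0.751, so P(X = 0) = 0.229.
  - Maximum: mass at X = 0, 2 and 3. Solving 2p₂ + 3p₃ = 0.93 and 4p₂ + 9p₃ = 2.361 gives p₃ = 0.167 and p₂ = 0.215, so P(X = 0) = 0.618.
- IANB: E[X] = 2.17 and E[X²] = 2.17² + 1.891² = 8.285.
  - Minimum: 0.
  - Maximum: mass at X = 0, 3 and 4. Solving 3p₃ + 4p₄ = 2.17 and 9p₃ + 16p₄ = 8.285 gives p₄ = 0.444 and p₃ = 0.132, so P(X = 0) = 0.425.

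| Share of children | ILA | IANB |
|---|---|---|
| SEM = 3, any shape | 22.9% to 61.8% | 0% to 42.5% |
| SEM = 3, single-peaked shapes | 28.5% to 56.4% | 0% to 30.0% |
| SEM of 4 or less, any shape | 56% to 98% | 13% to 72% |

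**Step 3: share with some sign of discomfort.** The ILA mean of 3.93 implies at least 1 − 0.618 = 38% and at most 1 − 0.229 = 77% of children above SEM = 3. Common smooth shapes give these SEM = 3 shares (ILA v IANB): negative binomial 48% v 19%, beta-binomial 50% v 22%, rounded normal 36% v 19%. Under these shapes, about half to two thirds of ILA children would still show a sign of discomfort.

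**Step 4: precision of a proportion at 25 per arm.** For 50% v 25%, the 95% half-width is 1.96 × √(0.25/25 + 0.1875/25) = 1.96 × √0.0175 = 0.259, about ±26 percentage points. Under the negative-binomial shape (48% v 19%), a test of proportions would have 61% power at 25 per arm; 80% power would need 39 per arm.

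**The case against.** The strongest reply is that only one word is out of line. The null hypothesis, the PICOT question and the sample size all concern less pain, and the planned tests match them. This stands, and it makes rewording the aim a legitimate alternative. It does not remove the mismatch, because the primary aim and the Abstract still speak of elimination and list comparison separately.

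SEM = 3 is a strict cut-off that the plan never adopts. The SEM table calls the grade 2 Eye sign one of anxiety and the grade 2 Sound only probable pain, so a numb but anxious child can score 4. This stands and calls for a sensitivity threshold.

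Some per-child counts are already planned: the three-face scale is qualitative and would be tabulated at extraction. But it grades satisfaction, is not tied to the primary aim and has no categorical test named.

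The data may not crowd the floor in both arms. The IANB planning mean is 2.17 above the minimum, and the Problems Anticipated section expects negative behaviour. If data are not normal, the Mann-Whitney test is not driven by a few high scorers. That is correct, but a rank test gives no pain-free count either.

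A reader might infer from the overlapping ranges that CC-ILA could well have the lower mean and also fewer pain-free children. The planning values permit this: for example, 8/25 at SEM = 3 with mean 3.96 under ILA against 10/25 with mean 5.16 under IANB. It needs unusual shapes, however. With single-peaked distributions the overlap shrinks to 28.5% v 30.0%, and all three smooth shapes keep the order of the means. Reversal is possible but unlikely, and the point does not depend on it.

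**Conclusion.** The point holds as a mismatch between the primary aim and what its analysis can support. A lower SEM mean or rank shows less pain; it does not show in how many children pain was absent. On the plan's own values the share at SEM = 3 is bounded only to 23-62% (ILA) and 0-42% (IANB), so a favourable mean is compatible with many CC-ILA children still showing discomfort.

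The figures assume that the planning scores are extraction scores on the 3-12 scale. The Sample size estimation does not say so, and the Introduction reports that the cited study measured both injection and extraction. They also come from intraligamentary anaesthesia that the Introduction describes as conventional, not computer-controlled.

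The documents do not support the stronger conclusion that the SEM comparison is invalid or should be replaced. It is a proper analysis of the less-pain question.

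**What to change.** Keep the SEM comparison as planned and add to the Statistical Analysis section:

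1. A prespecified supportive estimate: the number and proportion of children in each randomised arm with no sign of discomfort at extraction (SEM = 3), with the difference and its 95% CI (for example Newcombe). Repeat it for SEM of 4 or less as a sensitivity analysis. Report both beside the face-scale counts.
2. A counting rule for the analysis only, leaving clinical management as it is: a child in either arm whose allocated anaesthesia was supplemented or replaced because of pain after the injection was completed is counted as not pain-free. Report pain-related abandonment during injection separately, so that injection pain in one arm is not counted as failure at extraction. The plan describes replacement of anaesthesia for pain only for the experimental group, so any such event must be recorded in the same way in both arms.
3. A statement that the mean or rank comparison supports only a conclusion of less pain. Alternatively, reword the primary aim to match it.

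The cost is a few lines of text and one recorded item on supplementation; the SEM grades are already collected. The downside is precision (±26 percentage points for 50% v 25% at 25 per arm), so the proportion is an estimate beside the SEM comparison and not a replacement test.

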Method: The study will be a double-blind randomized controlled clinical trial, parallel design. A total of 50 healthy children aged 5-7 years, will be selected from Pediatric Dentistry and Dental Public Health Department, Faculty of Dentistry, Alexandria University, Egypt. Children will be selected with scores 3 or 4 Frankl behavioral rating scale. Each child selected will have at least one mandibular primary molar that is indicated for extraction. Written informed consent will be obtained from guardian. Participants will be randomly allocated into two groups according to the technique of anesthesia that will be used. Group I (test group) will receive CC-ILA, while group II (control group) will receive IANB. Heart rate will be used as vital parameter of pain, and will be recorded at base line, during injection and during extraction procedure. Pain reaction will be assessed objectively by two investigators using Sensory, Eye, Motor (SEM) scale, while subjectively the pain will be evaluated by asking the child to express his experience using a modified face scale from the Maunuksela scale.

Results: Data will be collected, tabulated and statistically analysed to obtain the results and conclusions of this study.

Keywords: Computer – controlled, Intraligamentary, Local anesthesia, Nerve block, Articaine, Pain, Extraction.

INTRODUCTION

Child management is a primary challenge facing pediatric dentists routinely. Uncooperative behaviour can significantly affect treatment quality, time, and increase the possibility of child injury during treatment as mentioned by Ingersoll and Ingersoll.⁽¹⁾ Acknowledgement of various behaviour management techniques, operating skills, and most importantly providing profound local anaesthesia are critical to deliver high quality dental service.⁽²⁾

Local anaesthetic (LA) forms the backbone of pain control techniques in dentistry. Although it is considered one of the painful procedures in daily dental practice, especially for children, however, its obligatory to use LA to eliminate pain during the various dental procedures and maintain child cooperation during the dental session.

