As the IANB anesthetizes a wide area other than the teeth, patients encounter loss of sensitivity, as well as total or partial loss of function of the facial muscles and tongue for the duration of the anaesthesia which may last up to two hours.⁽¹⁰⁾ Temporary hindering of patients' daily life with limited speech ability, eating, and most importantly, the risk of cheeks and lip biting are major drawback of this technique. Moreover, a rare but major complication of IANB anaesthesia is the injury of the mandibular nerve that could result in permanent impairment of the nerve function.^(11,12)

In an attempt to overcome the limitations of the IANB technique, other methods have been advocated such as Intraligamentary Anaesthesia (ILA). This technique was introduced by Chompret (1920).⁽¹⁶⁾ Intraligamentary Anaesthesia is a method of intra osseous injection with LA reaching the cancellous space in the bone via the periodontal ligament (PDL).

Intraligamentary Anaesthesia can be a very effective alternative technique in children, as it can help lessen the struggle of achieving successful anaesthesia during single tooth treatment.^(17, 18) It can have superior features in cases where anatomical variations are present and eliminating soft tissue injury which is a major concern while using other techniques. Moreover, it aids in treatment if teeth in different quadrants that are being summoned in a single visit, which helps both pediatric dentist and the child to avoid management complications associated with multiple dental visits. Many studies have proven that ILA does not cause any secondary complications if carefully applied. It causes very little pain if at all, rapid onset and allowing to start the dental work immediately.⁽¹⁹⁾

Nevertheless, it is believed that ILA has higher levels of post-operative pain than conventional techniques, and its duration only lasts for around 20 minutes.⁽²⁰⁻²²⁾ Two studies reported periodontal abscesses and deep pocket formation after ILA.^(23, 24) Hence, it should not be used for children suffering from cardiovascular problems as they are at more risk of developing subacute bacterial endocarditis.^(25, 26)

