Intraligamentary Anaesthesia is delivered manually via conventional, or high-pressure syringes,⁽²⁷⁾ or using computer-controlled local anaesthetic delivery systems (CCLADS).⁽²⁸⁾ There are some potential problems with the conventional intraligamentary technique. One such problem is the high pressure required to inject the anesthetic solution, which may lead to breakage of the glass cartridge with a conventional syringe.⁽²⁹⁾

The Wand-STA Single Tooth Anaesthesia is a CCLADS launched in 2006 by the manufacturers of the Wand Compudent system.⁽³⁰⁾ It's the only delivery system with incorporated dynamic pressure sensing (DPS) technology to monitor real-time pressure.⁽³¹⁾ It is capable of identifying the periodontal ligament tissue and enables the clinician to maintain the correct needle position within the periodontal ligament when performing ILA. Developed by [name], the STA-Intraligamentary Injection represents a new concept in local dental anesthesia techniques.⁽³²⁾

The system is activated by a foot control that allows a more precise and accurate LA delivery at a decreased steady pressure and volume via the intraligamentary route, regardless of the tissue resistance. This helps reduce tissue distortion and thus potentially minimizing the painful experience of ILA. However, it is significantly more expensive than a PDL-syringe and handling of the STA system may be complex for less trained dentists.⁽³³⁾

Garret-Bernardin and Cantile (2017)⁽³⁴⁾ showed that computerized injections are better tolerated and reduced pain perception in 7 – 15 year old patients compared to the traditional syringe during routine dental treatment.⁽³⁵⁾ In another study conducted on primary teeth, Tekin and Ersin (2012)⁽³⁶⁾ reported that a significantly higher mean Sound, Eye and Motor (SEM) score of pain reaction for IANB group was recorded in comparison to conventional ILA during both injection and extraction periods of mandibular primary teeth ($p < 0.005$).

Various studies report adequate anesthesia with computer controlled intraligamentary injection for primary tooth cavity preparation and pulpectomy as well as permanent tooth extraction.^(29, 33, 37-39) However, limited studies have been conducted to evaluate the efficacy of computer-controlled-ILA (CC-ILA) for extraction of primary molars.⁽³⁰⁾

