**** STA; Milestone Scientific, Inc., Livingston, NJ, USA

***** Zacurate, [name].

***** BeehiveSolutionsLtd: [name].

***** Likamed [name].

Figure (2): Wand - STA Single Tooth Anaesthesia Device

Randomization

Participants complying with the inclusion criteria will be randomly assigned using a computer-generated list of random numbers.⁽⁴⁹⁾

Allocation concealment

Each child included in the study will be given a serial number that will be used in the allocation. These numbers will be written in identical sheets of paper with the group to which each child is allocated and placed inside opaque envelopes carrying the respective names of the children.⁽⁵⁰⁾ A trial independent personnel will be assigned to the role of keeping the envelopes and unfolding them only at the time of the local anesthesia injection session so that the group the child is allocated to is concealed from the outcome evaluator.

Grouping

Participants will be randomly and equally allocated to one of the two arms (Figure 1).

- **Group I:** (experimental group n = 25) assigned to CC-ILA.
- **Group II:** (control group n = 25) assigned to conventional injection by IANB.

Blinding

The researcher (operator) who will perform all the injections and extractions as well as record heart rate measurements cannot be blinded to the type of intervention; a second impartial observer (evaluator) will record the Sensory, Eye, Motor (SEM) scale independently.⁽³⁰⁾ The statistician will be blinded to the treatment groups. Since the participants will also be blinded, therefore, the study will be triple-blind.

Examiner reliability

- For standardization, all clinical procedures will be performed by a single operator, who will be trained and calibrated for the Wand – STA system via training sessions by an expert through the manufacturing company, as it is too complex to be applied effectively without more appropriate training. Especially, the coordination between the foot pedal handling and the syringe has shown to be difficult.⁽³³⁾
- Training on heart rate measurement using the pulse oximeter will be also planned.

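### The plan claims a blind SEM evaluator and a triple-blind trial, but nothing in it masks, splits or orders the videotapes: injection SEM is very likely unblinded, and extraction SEM is not secured

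*Combined protocol and SAP*

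**What the plan says.** **Labels.** The abstract says "The study will be a double-blind randomized controlled clinical trial, parallel design". The Blinding section says the operator, who also records heart rate, cannot be blinded, that a second observer records SEM, and that the statistician is blinded. It concludes "Since the participants will also be blinded, therefore, the study will be triple-blind".

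**Protection of the evaluator.** Under Allocation concealment, an independent person keeps the envelopes, "unfolding them only at the time of the local anesthesia injection session so that the group the child is allocated to is concealed"; the sentence goes on to name the outcome evaluator as the person it is concealed from. Study Outcomes, B (Objective method) has a blind, impartial observer score SEM from the recorded tapes, for both injection and extraction.

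**Number of assessors.** The abstract says "Pain reaction will be assessed objectively by two investigators using Sensory, Eye, Motor (SEM) scale". The sections on Blinding, Examiner reliability and Study Outcomes all describe one observer.

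**Role of SEM.** The primary aim is to evaluate the computer-controlled intraligamentary technique (CC-ILA) "in eliminating pain during extraction of primary mandibular molars compared to Inferior Alveolar Nerve Block"; it names no instrument. The Sample size section uses SEM means to obtain the total "required to compare the effectiveness of CC-ILA technique versus IANB during extraction of primary mandibular molars". Pain during injection is a secondary aim.

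**The concern.** SEM is an observer's rating of sound, eye signs and movement, so a rater who knows the arm can shift it without intending to. The plan claims blinding for this rating. What it actually describes hides a sheet of paper from the evaluator, who then watches a recording of the procedure that the sheet names. If the recording shows the arm, concealing the sheet does not keep the rater blind.

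At stake is the credibility of the measure behind the sample size. The two labels and the two counts of assessors also leave a reader unsure what protection the final report could properly claim.

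**Working it through.** **1. What the tape can reveal, stage by stage**

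| Stage | CC-ILA | IANB | Plan section |
|---|---|---|---|
| Preparation | Child told to expect device sounds | Child told the cheek will feel different | Psychological child preparation |
| Injection | Handpiece, foot control, continuous tones | Syringe, lip or cheek shaken, added long buccal injection | Local Anaesthesia Administration |
| Numbness testing | Probe every 10 s | Probe every 30 s | Local Anaesthesia Administration |
| Extraction | Same forceps and technique | Same forceps and technique | Local Anaesthesia Administration |
| Pain during the procedure | Switch to IANB described | No switch described | Local Anaesthesia Administration |

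**2. Can the injection footage be masked?** SEM sums three items graded 1 to 4. Sound needs the audio track. Motor covers the hands, the body and turning of the head, so tight cropping would damage it. The cues therefore sit in material the rater needs. Camera framing is not described, so unblinding at injection is very likely rather than certain.

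**3. Can the extraction footage be masked?** Largely, because the technique is the same in both arms. Exposure requires the observer to have seen that child's injection or numbness testing first. No available section sets start and stop points, clip coding or a scoring order.

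**4. The plan's own sample size.** Inputs from Sample size estimation: means 3.93 and 5.17, SDs 1.223 and 1.891, alpha 5%, power 80%. Two-sided testing is assumed.
- Difference = 5.17 − 3.93 = 1.24.
- n per group = 2 × [SD × (1.960 + 0.842) / 1.24]².
- Simple mean of the SDs, (1.223 + 1.891)/2 = 1.557: n = 24.75, rounded up to 25. This reproduces the plan.
- Root-mean-square SD, √[(1.223² + 1.891²)/2] = 1.592: n = 25.89, rounded up to 26.

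**5. Illustration of scale.** Assume that knowing the arm raises one SEM item by one grade in k of the 25 children in one arm. The mean shift is k/25. With SD 1.592, the standard error is 1.592 × √(2/25) = 0.450. Rejection probabilities come from the two-sided noncentral t distribution with 48 df at 5%.

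| k | Shift | Share of 1.24 | False positives, no true difference | Power at 1.24, shift against | Power at 1.24, shift in favour |
|---|---|---|---|---|---|
| 0 | 0 | 0% | 5.0% | 77.0% | 77.0% |
| 3 | 0.12 | 10% | 5.8% | 68.3% | 84.1% |
| 6 | 0.24 | 19% | 8.2% | 58.5% | 89.6% |
| 12 | 0.48 | 39% | 18.1% | 38.0% | 96.3% |

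The 77.0% differs from the planned 80% because it uses the larger SD and the t distribution; with SD 1.557 the t-based power is 78.8%. A simulation of Welch's test with the two unequal SDs gave false-positive rates of 5.0%, 5.9%, 8.0% and 17.8% for k = 0, 3, 6 and 12. With integer scores, for k = 3, 6 and 12, the t-test gave 5.4%, 8.1% and 18.7% and the Mann-Whitney test 5.1%, 8.4% and 20.8%.

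Every k is an assumption. So is applying these SDs to extraction: the Sample size section does not state the phase, and the Introduction says the cited study found differences "during both injection and extraction periods of mandibular primary teeth".

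**The case against.** The strongest reply is that the plan does provide for a blind evaluator. That person is separate from the operator, is kept from the allocation and works from tapes. On this view the gap is an unwritten procedure, not an absence of blinding. This stands in part: the safeguards are real, and a competent team might split the tapes anyway. But calling an observer blind is not a mechanism, and for injection footage no obvious one exists that leaves the scale intact.

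Three stronger readings are tempting, and the documents do not support them.

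- *That the extraction comparison is biased.* This needs the observer to see arm-revealing footage first and then to score differently because of it. The documents establish neither.
- *That participants are certainly unblinded.* Children receive arm-specific information and undergo visibly different procedures, but a child aged 5 to 7 may not know what is being compared. What families are told may be in the consent form (Appendix II), which is not in the available text.
- *That the operator also scores SEM.* Only the abstract's mention of two investigators suggests it. Three later sections describe one observer, so this is probably a slip in the abstract.

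It is also fair to say that the numerical illustration is not evidence. The 18.1% requires 12 of 25 children in one arm, 48%, to be mis-scored in the same direction. At 3 children the rate is 5.8%.

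**Conclusion.** The point holds at moderate weight. The blinding the plan claims is very likely not delivered for injection SEM and is not secured for extraction SEM. The first is an inference from the cues described and the content of the scale. The second is conditional on viewing order, which the plan leaves open.

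The size and direction of any bias are unknown. Under the assumed shifts of 0.24 and 0.48 points, false positives rise from 5% to about 8% and 18%; with a true difference of 1.24, power could fall or rise depending on direction. The conclusion does not rest on those figures, and the sample size is unaffected.

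The label conflict and the differing assessor counts stand as textual inconsistencies. The absence of a masking procedure is judged on the available text, without the flow chart or the consent form.

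**What to change.** 1. **Clips and order.** Have someone other than the operator and the evaluator, such as the independent envelope keeper, cut each tape into an injection clip and an extraction clip. That person knows the arm, so one written start and end rule must apply to both arms, with the extraction clip starting at first forceps application. Code the clips, put them in random order, and have the evaluator score every extraction clip before any injection clip.
2. **Children switched to IANB.** Fix one scoring rule in advance that keeps the IANB injection out of the extraction clip but still records the pain that led to the switch, including pain before forceps application. Without it, the injection would reveal the arm and mix injection reaction into extraction SEM. Keep these children in their randomised arm and report their number as a residual unblinding cue.
3. **One blinding statement.** Replace both labels with: operator, who also records heart rate, unblinded; statistician blinded; extraction SEM evaluator masked as far as the clips allow; injection SEM treated as unblinded; participant blinding claimed only as far as the information given to families supports it.
4. **Assessors.** Reconcile the abstract's two investigators with the single observer described elsewhere.

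**Cost.** Fifty tapes become 100 clips, with modest editing and no extra visits. Scoring waits until the last procedure, which the timetable allows: procedures run in months 5 to 8, data management and analysis in months 9 to 11. The triple-blind label is lost. Residual cues remain in switched children, and possibly in IANB children, for whom the Introduction describes "total or partial loss of function of the facial muscles and tongue".
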